- An event that is considered to be due to ipilimumab, such as immune related AEs that are grade 2 or less can receive corticosteroids if deemed clinically necessary so as long as they are tapered off by next dose. If ipilimumab dosing must be delayed for > 4 weeks ($+/ - 3$ days for holiday or scheduling logistics) (more than 8 weeks since the prior dose administration) for any of the above reasons, patients must come off treatment.
- Decitabine may continue if AE considered to be due to ipilimumab

If there is a dose delay in ipilimumab:

For any dose delay, patients must re-meet laboratory criteria (including complete blood count with differential and platelets, comprehensive metabolic profile including liver enzymes) to be treated again on day of therapy (prior to dosing).

Resuming ipilimumab:

- Should coincide with day 1 of treatment cycle.
- If the adverse event is suspected to be due to ipilimumab, then the AE must resolve to \leq grade 1 severity or returns to baseline within 4 weeks of initiating the dose delay (no more than 8 weeks since the most recent prior dose administration). This includes immune-related AE. Patients must be tapered off prednisone prior to resuming ipilimumab.
- If the *adverse event has resolved to \leq grade 1*, ipilimumab dosing may be restarted at the next scheduled time point per protocol. Please see suggested guidelines for management of specific immune related adverse events (see [Appendix C](#)). Please note that re-initiating treatment may be associated with recurrence or exacerbation of autoimmune or inflammatory events. In some instances clinical resolution of events such as colitis may be associated with residual pathologic changes and should require evaluation of complete resolution prior to restarting therapy.
- If ipilimumab dosing must be delayed for > 4 weeks ($+/- 3$ days for holiday or scheduling logistics) (more than 8 weeks [$+/- 3$ days] since the prior dose administration) for any of the above reasons, patients must come off treatment.

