- Autoimmune/inflammatory events are presumably related to the mechanisms of action of ipilimumab and potentially to a therapeutic effect. The incidence and severity of these events may be dose related, but once initiated, there is no evidence that lowered doses can be administered without continued autoimmune activity and there has so far been no demonstrable benefit to continuing ipilimumab after an autoimmune event during the initial treatment. The significance and benefit of toxicity or continued treatment in the maintenance phase has not been determined. Typically no dose modification is used for ipilimumab.

Permanent Discontinuation of Ipilimumab for Related Adverse Events

If discontinuing ipilimumab, participants will have the option to continue decitabine alone on study if they are determined to be clinically benefitting from treatment at the investigator's discretion.

Permanently discontinue ipilimumab for any of the following:

- Grade III or higher acute GVHD.
- Persistent adverse reactions that requires holding more than 2 ipilimumab doses (exception: patients with a GVH event(s) that is determined to be less than a grade III who are benefitting from study treatment can continue on study after approval from overall PI).
- Any persistent grade 3 or 4 event (see exceptions below in [section 6.2.1](#)).
- Any immune related AE that is grade 3 or higher requiring systemic corticosteroids at a dose of 1 to 2 mg/kg/day of prednisone or equivalent. Immune related AEs that were

grade 2 or less are allowed to stay on study and receive corticosteroids if necessary so as long as they are tapered off by next scheduled dose of ipilimumab. They cannot be delayed by more than 4 weeks (meaning 8 weeks between doses), or they have to come off study.

- Severe or life-threatening adverse reactions, including any of the following:
 - Colitis with abdominal pain, fever, ileus, or peritoneal signs; increase in stool frequency (7 or more over baseline), stool incontinence, need for IV hydration for more than 24 hours, gastrointestinal hemorrhage, and gastrointestinal perforation
 - Aspartate aminotransferase (AST) or alanine aminotransferase (ALT) >5 times the upper limit of normal or total bilirubin >3 times the upper limit of normal
 - Stevens-Johnson syndrome, toxic epidermal necrolysis, or rash complicated by full thickness dermal ulceration, or necrotic, bullous, or hemorrhagic manifestations

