 - Severe motor or sensory neuropathy, Guillain-Barré syndrome, or myasthenia gravis
 - Severe immune-mediated reactions involving any organ system (e.g., nephritis, pneumonitis, pancreatitis, non-infectious myocarditis)
 - Immune-mediated ocular disease that is unresponsive to topical immunosuppressive therapy
 - Any adverse event, laboratory abnormality or intercurrent illness which, in the judgment of the investigator, presents organ specific injury and/or a substantial clinical risk to the patient with continued dosing.

The following neurological adverse event requires permanent discontinuation of ipilimumab and defines unacceptable neurotoxicity:

- Any motor neurologic toxicity >/= grade 3 regardless of causality
- Any >/= grade 3 treatment related sensory neurologic toxicity

Please refer to [Appendix C](#) and the Investigator Brochure for suggested specific treatment algorithms.

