6.2.1 Exceptions to Permanent Discontinuation

- Potentially reversible inflammation (< grade 4), attributable to a local anti-tumor reaction and a potential therapeutic response. This includes inflammatory reactions at sites of tumor resections or in draining lymph nodes, or at sites suspicious for, but not diagnostic of metastasis.
- Hospitalization for neutropenic fever evaluation (this is a common adverse event of underlying disease and of decitabine).
- Hospitalization for \leq grade 2 adverse events where the primary reason for hospitalization is to expedite the clinical work-up.
- Patients with the following conditions where in the investigator's opinion continuing study drug administration is justified based on the potential for continued clinical benefit:

- Patients treated with systemic steroids for less than 4 weeks without evidence of autoimmune disease requiring steroids treatment
- Grade 2 skin rash treated with topical steroids for less than 4 weeks
- Grade 2 Ocular toxicity that has completely responded to topical therapy within 4 weeks
- Endocrinopathies where clinical symptoms are controlled with appropriate hormone replacement therapy. **Note:** Ipilimumab may not be restarted while the patient is being treated with systemic corticosteroids except for patients on stable doses of hormone replacement therapy such as hydrocortisone.

6.2.2 Immune-Related Adverse Events (irAEs)Reactions and Immune-mediated Adverse Reactions: Definition, Monitoring, and Treatment

These are suggested guidelines for the management of immune-related adverse events. For the purposes of this study, an immune-related adverse reaction is defined as an adverse reaction of unknown etiology associated with drug exposure and consistent with an immune phenomenon. Efforts should be made to rule out neoplastic, infectious, metabolic, toxin or other etiologic causes prior to labeling an event an irAEs. Serologic, immunologic, and histologic (biopsy) data should be used to support the diagnosis of an immune-related toxicity. Suspected immune-related adverse reactions must be documented on an AE or SAE form. Another term for an irAE is an immune-mediated adverse reaction, as it is termed in the Ipilimumab US Prescribing Information. Both terms may be used in this protocol document.

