6.4.2 Immune-mediated Hepatitis and Pancreatitis

Hepatic immune-related AEs were mostly clinically silent and manifested as transaminase or bilirubin laboratory abnormalities. Fatal hepatic failure has been reported in clinical trials of ipilimumab. **Serum transaminase and bilirubin and lipase levels must be evaluated before each dose of ipilimumab as early laboratory changes may be indicative of emerging immune-related hepatitis/ pancreatitis and elevations in liver function tests (LFTs) may develop in the absence of clinical symptoms.** Increase in LFT or total bilirubin should be evaluated to exclude other causes of hepatic injury, including infections, disease progression, or other medications, and monitored until resolution. Liver biopsies from patients who had immune-related hepatotoxicity showed evidence of acute inflammation (neutrophils, lymphocytes, and macrophages).

Monitor liver function tests (hepatic transaminase and bilirubin levels, lipase) and assess patients for signs and symptoms of hepatotoxicity/ pancreatitis before each dose of ipilimumab. In patients with hepatotoxicity, rule out infectious or malignant causes and increase frequency of liver function test monitoring until resolution. Withhold ipilimumab in patients with grade 2 hepatotoxicity.

Permanently discontinue ipilimumab in patients with grade 3–5 hepatotoxicity/pancreatitis and administer systemic corticosteroids at a dose of 1 to 2 mg/kg/day of prednisone or equivalent. When liver function tests show sustained improvement or return to baseline, initiate corticosteroid tapering and continue to taper over 1 month. Across the clinical development program for ipilimumab, mycophenolate treatment has been administered in patients who have persistent severe hepatitis despite high-dose corticosteroids.

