APPENDIX C

MANAGEMENT OF IMMUNE-RELATED ADVERSE EVENTS,
DIARRHEA, HEPATOTOXICITY, ENDOCRINOPATHY, SKIN
AND NEUROPATHY *

*Investigator's Brochure (March 2016)

[figure not shown]
General Recommendations for Management of Suspected Inflammatory Events

* Based on clinical experience to date, systemic steroids for treatment of irAEs do not appear to impact the development or maintenance of ipilimumab clinical activity in advanced melanoma.

Diarrhea Management Algorithm

GI Toxicity Management Algorithm

Patients on IV steroids may be switched to oral corticosteroid (e.g., prednisone) at an equivalent dose at start of tapering or earlier, once sustained clinical improvement is observed. Lower bioavailability of oral corticosteroids should be taken into account when switching to the equivalent dose of PO corticosteroids.

Diarrhea				
GRADE 1	GRADE 2	GRADE 3	GRADE 4	GRADE 5
Increase of <4 stools per day over baseline; mild increase in ostomy output compared with baseline	Increase of 4-6 stools per day over baseline; IV fluids indicated < 24 hrs; moderate increase in ostomy output compared to baseline; not interfering with activities of daily living (ADL)	Increase of ≥7 stools per day over baseline; incontinence; IV fluids ≥ 24 hrs; hospitalization; severe increase in ostomy output compared to baseline; interfering with ADL	Life-threatening consequences (e.g., hemodynamic collapse)	Death

[figure not shown]
Hepatotoxicity Management Algorithm

Situation: rising liver function tests (LFTs) >8X ULN or suspected immune-mediated hepatitis

- 1) Admit subject to hospital for evaluation and close monitoring
- 2) Stop further ipilimumab dosing until hepatotoxicity is resolved. Consider permanent discontinuation of ipilimumab per protocol
- 3) Start at least 120 mg methylprednisolone sodium succinate per day, given IV as a single or divided dose
- 4) Check liver laboratory test values (LFTs, T-bilirubin) daily until stable or showing signs of improvement for at least 3 consecutive days
- 5) If no decrease in LFTs after 3 days or rebound hepatitis occurs despite treatment with corticosteroids, then add mycophenolate mofetil 1g BID per institutional guidelines for immunosuppression of liver transplants (supportive treatment as required, including prophylaxis for opportunistic infections per institutional guidelines)
- 6) If no improvement after 5 to 7 days, consider adding 0.10 to 0.15 mg/kg/day of tacrolimus (trough level 5-20 ng/mL)

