- 7) If target trough level is achieved with tacrolimus but no improvement is observed after 5 to 7 days, consider infliximab, 5 mg/kg, once
- 8) Continue to check LFTs daily for at least 2 weeks to monitor sustained response to treatment

A flow chart of the algorithm is depicted on the following page.

Hepatotoxicity Management Algorithm

[figure not shown]
*Ipilimumab may be held/delayed rather than discontinued if AST/ALT $\leq 8 \times$ ULN and Tbili $\leq 5 \times$ ULN. Resume ipilimumab when AST/ALT/Tbili return to grade 2 and meet protocol specific retreatment criteria.

**The recommended starting dose for grade 4 hepatitis is 2 mg/kg/day methylprednisolone IV.

*** MMF, mycophenolate mofetil

Patients on IV steroids may be switched to oral corticosteroid (e.g., prednisone) at an equivalent dose at start of tapering or earlier, once sustained clinical improvement is observed. Lower bioavailability of oral corticosteroids should be taken into account when switching to the equivalent dose of PO corticosteroids.

Endocrinopathy Management Algorithm

[figure not shown]

↑

Patients on IV steroids may be switched to oral corticosteroid (e.g., prednisone) at an equivalent dose at start of tapering or earlier, once sustained clinical improvement is observed. Lower bioavailability of oral corticosteroids should be taken into account when switching to the equivalent dose of PO corticosteroids.

[figure not shown]
*Patients with adrenal insufficiency might need to continue steroids with mineralocorticoid component as substitution

Skin Toxicity Management Algorithm

Patients on IV steroids may be switched to oral corticosteroid (e.g., prednisone) at an equivalent dose at start of tapering or earlier, once sustained clinical improvement is observed. Lower bioavailability of oral corticosteroids should be taken into account when switching to the equivalent dose of PO corticosteroids.

Neurological Toxicity Management Algorithm

Patients on IV steroids may be switched to oral corticosteroid (e.g., prednisone) at an equivalent dose at start of tapering or earlier, once sustained clinical improvement is observed. Lower bioavailability of oral corticosteroids should be taken into account when switching to the equivalent dose of PO corticosteroids.

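### Section 6.2 requires ipilimumab to be stopped permanently at AST/ALT above 5x or bilirubin above 3x ULN, but an Appendix C footnote allows a hold up to 8x and 5x ULN, and nothing says which governs

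*Combined protocol and SAP*

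**What the plan says.** **Section 6.2, permanent discontinuation for related adverse events.** The list opens with "Permanently discontinue ipilimumab for any of the following". Under severe or life-threatening reactions it includes AST or ALT ">5 times the upper limit of normal or total bilirubin >3 times the upper limit of normal".

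**Section 6.2.1, exceptions.** These cover reversible inflammation below grade 4 from a local anti-tumor reaction, two kinds of hospitalization, and a group of conditions where the investigator judges that "continuing study drug administration is justified based on the potential for continued clinical benefit". That group consists of short steroid courses without autoimmune disease, grade 2 rash, grade 2 ocular toxicity and controlled endocrinopathies. No exception concerns liver tests.

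**Section 6.4.2, hepatitis.** "Withhold ipilimumab in patients with grade 2" hepatotoxicity is the only hold. Grades 3 to 5 call for a permanent stop. Section 6.2.2 likewise calls for a permanent stop at grade 3 or 4 immune-mediated toxicity.

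**Appendix C, hepatotoxicity algorithm.** For liver tests above 8 times ULN or suspected immune-mediated hepatitis, step 2 reads "Stop further ipilimumab dosing until hepatotoxicity is resolved. Consider permanent discontinuation of ipilimumab per protocol". The footnote to the flow chart says "Ipilimumab may be held/delayed rather than discontinued if AST/ALT" is at or below 8 times ULN and total bilirubin is at or below 5 times ULN. Dosing resumes once values return to grade 2 and the protocol's own retreatment criteria are met.

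**The concern.** The stop limits in section 6.2 lie inside the hold range of the footnote, so some patients fall under both rules, and the rules give opposite answers. Appendix C is attributed to the Investigator's Brochure, and its footnote has not been adapted to the limits this protocol sets.

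The issue is patient safety. The protocol itself reports fatal hepatic failure with ipilimumab (sections 2.2 and 6.4.2) and warns in section 6.2 that restarting may bring immune events back or worsen them. Liver events are foreseeable here. High-grade liver immune events occurred in 6.8% of melanoma patients on 10 mg/kg monotherapy (section 2.2). Chronic liver GVHD was dose-limiting at both 3 and 10 mg/kg in the earlier post-transplant study (section 2.4). Neither figure estimates how often a patient would fall in the disputed range.

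**Working it through.** The plan states no figure to reproduce. The check is a comparison of thresholds, all in multiples of ULN.

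**Inputs**

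- Section 6.2, permanent stop: AST/ALT > 5 **or** bilirubin > 3, for related events.
- Appendix C footnote, hold allowed: AST/ALT ≤ 8 **and** bilirubin ≤ 5.
- Section 6.2, resuming: the event is back to grade 1 or less or to baseline within 4 weeks of starting the delay, no more than 8 weeks have passed since the last dose, and the patient is off prednisone.
- Appendix F, limits before each ipilimumab dose: AST/ALT ≤ 3.0 and bilirubin ≤ 1.5 (≤ 3.0 with Gilbert's disease or disease-related hemolysis).

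**Overlap.** Both rules apply when (AST/ALT > 5 or bilirubin > 3) and (AST/ALT ≤ 8 and bilirubin ≤ 5). This gives two ranges:

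1. AST/ALT above 5 and up to 8, with bilirubin up to 5.
2. Bilirubin above 3 and up to 5, with AST/ALT up to 8.

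**Illustrative patients with a related event**

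| AST/ALT | Bilirubin | Section 6.2 numeric limit | Appendix C footnote | Conflict? |
|---|---|---|---|---|
| 4 | 1 | Not reached | Hold allowed | No |
| 6 | 1 | Permanent stop | Hold allowed | Yes |
| 2 | 4 | Permanent stop | Hold allowed | Yes |
| 9 | 1 | Permanent stop | Hold not allowed | No |
| 6 | 6 | Permanent stop | Hold not allowed | No |

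**Do the restart rules close the gap?** No. They ask whether the patient has recovered. Someone who peaked at 6 and returned to grade 1 within 4 weeks, off prednisone and inside the Appendix F limits, satisfies all of them. Section 6.2 bars the next dose whatever the recovery. The footnote's return to grade 2 is not counted as a second conflict, because the footnote also requires the protocol's retreatment criteria, and those bring in the stricter rule.

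**Is precedence stated?** No sentence in section 6 or Appendix C says so. On resuming, section 6.2 says "Please see suggested guidelines for management of specific immune related adverse events" and points to Appendix C. After the stop list it refers to Appendix C "and the Investigator Brochure for suggested specific treatment algorithms". Appendix F sends sites with abnormal liver tests to section 6 and to the Appendix C algorithms.

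**Effect on the primary endpoint.** The DLT definition in section 5.2 turns on grade, relatedness and recovery. Whether ipilimumab was held or stopped does not enter it, so DLT counts and escalation decisions do not change.

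**The case against.** The strongest reply is that section 6.2 plainly governs. It is imperative, it says delay decisions rest on the criteria it specifies, and sections 6.2.2 and 6.4.2 repeat the permanent stop by grade. Appendix C is called suggested or helpful throughout, and its footnote only permits a hold. A site that follows section 6.2 breaches nothing in the appendix. The cross-references can also be read as pointing to how an event is treated, not to a rival stopping rule. This makes section 6.2 the likelier reading, but it does not remove the contradiction. The words deferring to the protocol in step 2, and in the footnote's restart sentence, do not attach to the sentence that replaces discontinuation with a hold.

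A second reply is oversight. Re-introduction is discussed with the overall PI (section 6), held doses are reviewed on calls, grade 3 or higher related events are e-mailed to the PI (section 7.3.3), and suspected immune events go to central review (section 7.3.5). These lower the chance of a wrong re-dose. They are not a firm barrier: calls are planned at a minimum of every 4 to 6 weeks while induction dosing is every 4 weeks, and the e-mail for a grade 3 event has no stated deadline.

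Third, the flow chart is not reproduced in the text reviewed, so the box carrying the asterisk cannot be seen. That leaves some uncertainty about context, but the footnote is a complete instruction on its own.

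Finally, section 6.2 applies to related events only, and acute GVHD of overall grade III or higher already requires a permanent stop. Both points narrow the group affected. Neither empties it.

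**Conclusion.** The concern holds. For a related event with AST/ALT above 5 and up to 8 times ULN (bilirubin up to 5), or bilirubin above 3 and up to 5 times ULN (AST/ALT up to 8), the protocol gives two dosing instructions that cannot both be followed. The conflict is in the text for both arms and all four ipilimumab levels (1, 3, 5 and 10 mg/kg), at most 24 patients per arm and 48 in total. That is the population under the conflicting text, not an estimate of how many would be affected; the documents do not support such an estimate. The conclusion assumes that the unseen flow chart does not itself subordinate the footnote to section 6.2. It is a safety wording error that should be corrected. It does not threaten the design or the primary endpoint.

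**What to change.** Reword the Appendix C footnote along these lines:

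> Ipilimumab may be held instead of discontinued only while AST/ALT is ≤ 5x ULN and total bilirubin is ≤ 3x ULN. Above either limit, discontinue permanently (section 6.2). Resume only when the event is back to grade 1 or less or to baseline (section 6.2) and the Appendix F pre-dose limits are met.

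Add at the head of Appendix C:

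> Where this appendix differs from section 6, section 6 governs.

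Appendix F needs no change. The cost is one footnote and one sentence, both restating limits the protocol already sets. Design, data collection and analysis are untouched.

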APPENDIX D ACUTE MYELOID LEUKEMIA RESPONSE CRITERIA

Cheson, B et al., J Clin Oncol, 2003, 4642-9.

Morphological Complete Remission (CR):

-Normalization of the peripheral blood absolute neutrophil count $> 1.0 \times 10^9/L$, platelets $>$ than $100 \times 10^9/L$ no residual evidence of extramedullary disease and bone marrow aspirate with $\leq 5\%$ blasts, no blasts with Auer rods

Morphological Complete Remission with incomplete blood count recovery (CRi):

-Same as CR but without normalization of the peripheral blood absolute neutrophil and platelet count

Relapse from CR or CRi:

-Reappearance of leukemic blasts in the peripheral blood; or $> 5\%$ blasts in the bone marrow not attributable to another cause (e.g. recovery of normal cells following treatment-induced aplasia or use of growth factors) OR
-Appearance or reappearance of extramedullary disease.
-If there are no circulating blasts and no extramedullary disease and the bone marrow blast percentage is $> 5\%$ but $< 20\%$, then a repeat bone marrow performed at least 7 days after the first marrow examination and documenting bone marrow blast percentage $> 5\%$ is necessary to establish relapse.

Partial Remission (PR):

-Normalization of the peripheral blood absolute neutrophil count $1.0 \times 10^9/L$, platelets $>$ than $100 \times 10^9/L$, and at least a 50% decrease in the percentage of marrow aspirate blasts to 5-25%, or marrow blasts $< 5\%$ with Auer rods.

Cytogenetic Responses

Complete cytogenetic response: An abnormal clone is detected in all metaphases prior to treatment and only normal metaphases are observed in all metaphases following treatment.

Partial cytogenetic response: An abnormal clone is detected in all metaphases prior to treatment and the post-treatment sample has 50% or fewer abnormal metaphases compared to the pretreatment value.

Cytogenetic non-response: An abnormal clone is detected in all metaphases prior to treatment and neither complete nor partial cytogenetic response is observed in post-treatment specimens. Specimens with normal cytogenetic results before treatment will not be evaluated for cytogenetic response. The method used to determine cytogenetic response will be standard metaphase cytogenetics.

Stable disease:

-Subjects who fail to achieve CR, CRi, or PR and who do not have criteria for PD will be defined as having the stable disease. If the subject dies prior to response assessment at the end of Cycle 1, then they will be classified as "indeterminate".

Progressive disease (PD): may be defined as ONE of the following:

- >50% increase in peripheral blood or bone marrow blasts from best assessment with minimum threshold of 20% blasts in the marrow or $1.0 \times 10^9/L$ blasts in peripheral blood.
- Development of biopsy proven extramedullary leukemia (if the subject has extramedullary disease at baseline, then PD will be defined by blood and marrow criteria or if new sites of extramedullary disease appear).
- If subject who present with an initial marrow blast percentage sufficiently high to preclude the ability to base disease progression on a >50% increase in marrow blast percentage, disease progression should be based on peripheral blood criteria or development of extramedullary leukemia as above.

Persistent Disease

Hematologic Persistence – Bone marrow or peripheral blasts >5% after d+30 following alloSCT

